## **XX. STATISTICAL CONSIDERATIONS**

The objective of this study is to assess the efficacy and safety of treatment of E7070 with chemotherapy in Leukemia patients. The efficacy will be measured by the overall response (CR + CRp + PR+ marrow clearance of blast) during Cycle 1. The sample size and stopping rules will be determined according to Simon's two-stage design.

The efficacy will be assessed based on the Simon's two-stage Minmax design. The new treatment will be considered promising if the response rate is 25% or higher, and will be considered unworthy of further investigation if response rate is 10% or less. The maximum sample size of 40 patients is chosen to differentiate between response rates of 10% and 25% with 90% power at a significance level of 0.1. In particular, 27 patients will be enrolled at the first stage. If there are two or fewer patients with response, the trial will be terminated; otherwise another 13 patients will be treated for a total of 40 patients. If, among 40 patients, there are 6 or fewer patients with response, the treatment will be concluded ineffective. The probability of early termination due to futility is 0.48.

A Bayesian sequential monitoring method will be used to monitor the toxicity. We stop the trial if the toxicity is likely to be greater than 33%. That is, stop the trial if

$$\text{Prob \{toxicity rate > 33\% | data\}} > 0.80.$$

The prior distribution of toxicity rate is assumed to be beta (0.67, 1.33). Following this rule, the trial will be terminated due to toxicity if  $[\# \text{ toxicity}]/[\# \text{ patients evaluated}] \geq 2/3, 3/5, 4/7, 5/10, 6/13, 7/15, 8/18, 9/20, 10/23, 11/26, 12/28, 13/31, 14/34, 15/37, \text{ or } 16/40$ .

A toxic event will be defined as death or a CTCAE 4.0 grade 3/4 non-hematological toxicity related to study drug lasting or 7 days or more.

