Descriptive statistical analysis will be calculated, including histograms or box-plots, proportions, range, means and standard deviations. Fisher's exact test and Wilcoxon rank test will be used in univariate analyses of categorical and continuous variables, respectively. Overall response (CR + CRp + PR) rate and its 95% confidence interval will be estimated using a binomial distribution. Overall survival and progression free survival functions will be estimated using the Kaplan-Meier method. The two-sided log-rank test will be used to examine the difference of survival functions among different groups. Toxicity will be reported by type, frequency and severity. Worst toxicity grades per patient will be tabulated for selected adverse events and laboratory measurements.

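### The plain binomial estimate and 95% CI ignore the two-stage stopping rule; the effect on reporting is minor and matters only if the trial ends with 3 to 6 responders of 40

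*Combined protocol and SAP*

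**What the plan says.** Section XX (Statistical Considerations) names the design: "The efficacy will be assessed based on the Simon's two-stage Minmax design". The upper benchmark is worded as "The new treatment will be considered promising if the response rate is 25% or higher". At the lower benchmark of 10%, the combination is not worth pursuing. The two are to be separated "with 90% power at a significance level of 0.1". Stage 1 takes 27 patients, and its rule reads: "If there are two or fewer patients with response, the trial will be terminated; otherwise another 13 patients will be treated". With 6 or fewer responders among 40, the treatment is judged ineffective. The stated probability of early termination is 0.48.

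The response that enters this rule is CR + CRp + PR + marrow clearance of blasts during Cycle 1.

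The last paragraph of the same section gives the estimation method: "Overall response (CR + CRp + PR) rate and its 95% confidence interval will be estimated using a binomial distribution". It does not mention the two stages or say which binomial interval is meant. Its response definition omits marrow clearance, so it is narrower than the definition used for stopping.

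**The concern.** Once the futility rule is applied, the final count of the stopping endpoint is not a draw from a binomial with 40 patients. Trials with 0, 1 or 2 responders of 27 end there. Every total out of 40 must include at least 3 responders among the first 27. A plain binomial gives weight to paths that the design forbids, such as 1 responder in the first 27 followed by 3 in the next 13.

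Response is a primary objective, and its rate and interval will be reported whatever the decision. What is at stake is whether a modest result is described correctly relative to the plan's own 10% and 25% benchmarks. The affected region is plausible: Section II puts response in this population at under 10% to 20%.

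**Working it through.** **Inputs, all from Section XX.** n1 = 27, stop if X1 ≤ 2; 13 more patients, n = 40; ineffective if the total is ≤ 6; p0 = 0.10, p1 = 0.25. Assumptions: the estimated endpoint is the stopping endpoint, there is no toxicity stop, and enrolment is exactly 27 or 40. The interval type is not stated, so the exact (Clopper-Pearson) interval is taken as the plain method.

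**Step 1: reproduce the design.** Early termination at 10% = P(X1 ≤ 2) = 0.0581 + 0.1744 + 0.2520 = 0.4846 from 0.0005-level rounding of each term (plan: 0.48). The chance of passing is the sum over x1 ≥ 3 of b(x1; 27, p) × P(X2 ≥ 7 − x1; 13, p). It is 0.0977 at 10% (plan: 0.1) and 0.9001 at 25% (plan: 90%). The design is sound.

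**Step 2: average bias of the plain rate** (x/27 if stopped, x/40 otherwise). Because E[X1] = 27p, the bias reduces to

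bias = −(1/27 − 1/40) × Σ over x1 ≤ 2 of b(x1; 27, p) × (27p − x1).

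At p = 0.10: 1/27 − 1/40 = 13/1080 = 0.01204. The sum is 0.0581 × 2.7 + 0.1744 × 1.7 + 0.2520 × 0.7 = 0.630. The bias is −0.0076, or −0.76 points. The same formula gives −0.61 at 15%, −0.32 at 20%, −0.12 at 25% and −0.04 at 30%. The largest value is −0.76, near 10.7%.

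**Step 3: coverage of the exact binomial interval under the two-stage rule.** It is 98.5% at 10%, 97.6% at 15%, 96.2% at 20%, 96.0% at 25% and 96.0% at 30%. The minimum is at 24.3%, just above the upper limit for 2/27. There, every stage-1 stop and also 3/40 and 4/40 give intervals wholly below the truth: 0.0249 + 0.0014 + 0.0086 = 0.0349 (nominal 0.025). Intervals wholly above the truth add 0.0203. Coverage is 1 − 0.0349 − 0.0203 = 0.9448. It is below 95% only at about 24.3 to 24.9% and 26.8 to 27.0%.

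**Step 4: results by outcome.** The uniformly minimum-variance unbiased estimate (UMVUE) for total s is Σ C(26, x−1) C(13, s−x) divided by Σ C(27, x) C(13, s−x), both over x ≥ 3. For s = 3 it is 325/2925 = 11.1%. For s = 4 it is (325 × 13 + 2600)/(2925 × 13 + 17550) = 6825/55575 = 12.3%. The two-stage limits come from setting each tail probability of the true two-stage distribution to 0.025, with stage-1 stops ranked below all totals out of 40.

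| Outcome | Plain rate (95% CI) | Two-stage (95% CI) |
|---|---|---|
| 2/27 | 7.4% (0.9 to 24.3) | identical |
| 3/40 | 7.5% (1.6 to 20.4) | 11.1% (2.4 to 24.5) |
| 4/40 | 10.0% (2.8 to 23.7) | 12.3% (3.2 to 25.5) |
| 5/40 | 12.5% (4.2 to 26.8) | 13.8% (4.4 to 27.5) |
| 6/40 | 15.0% (5.7 to 29.8) | 15.7% (5.8 to 30.1) |
| 7/40 | 17.5% (7.3 to 32.8) | 17.8% (7.4 to 32.8) |

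The plain upper limits are out of order. A trial stopped at 2/27 has 24.3%, while one that passes stage 1 and ends at 3/40 has 20.4%. The two-stage limits rise in order: 24.3, 24.5, 25.5. Only at 4/40 does the exclusion of 25% change.

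**Step 5: how often this arises.** P(3 to 6 of 40) at 10% = 0.0593 + 0.1252 + 0.1344 + 0.0988 = 0.42. It is 0.40 at 15%, 0.22 at 20% and 0.08 at 25%.

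**The case against.** The case for leaving the text alone is strong on size. The average bias is small beside the root-mean-square error of the plain rate, which is 5.2 points at 10%, 6.8 at 20% and 7.1 at 25%. The decision is made by count, so the results that differ, 3 to 6 of 40, already have a verdict. Stage-1 stops are identical under both methods. Only 4/40 changes whether 25% is excluded, and at a true rate of 25% that outcome has probability 0.7%. All of this stands, and it limits the point to reporting.

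The unbiased estimate is also not plainly better. At 10% its root-mean-square error is 5.4 points against 5.2 for the plain rate, although it is slightly smaller at 15 to 30%. Among trials that reach 40 patients, the plain rate is on average too high (by 3.1 points at a true rate of 10%), and the unbiased estimate more so (4.5). The downward bias holds only when averaged over stopped trials as well. This is a reason to show both estimates.

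The most substantial objection is the endpoint. The estimation sentence covers CR + CRp + PR, which is not the stopping endpoint. Marrow clearances could carry a trial past stage 1, so for the narrower definition low totals out of 40 are not restricted as described. The outcome table therefore applies to the stopping endpoint only. If CR + CRp + PR were a fixed share of stopping responses, the bias would shrink in proportion. At an assumed share of 0.75 it would be 0.57 points when the stopping-endpoint rate is 10%.

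What remains is that the plan specifies no interval consistent with its own stopping rule, and that the plain limits are out of order just above the futility boundary.

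**Conclusion.** The point holds as a minor reporting matter. For the stopping endpoint, the plain binomial ignores the design. The cost is at most 0.8 points of average bias and at most about half a point of coverage in two narrow bands. At 3 to 6 of 40, the estimate shifts by up to 3.6 points (11.1 − 7.5) and the upper limit by up to 4.1 (24.5 − 20.4).

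A reader might infer three stronger conclusions, and the documents support none of them:

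- That the 95% interval generally fails to reach its stated coverage. The exact interval is conservative at nearly all true rates. A Wald interval would do worse (87.4% at a true rate of 20%), but the plan does not name one, and in a fixed sample of 40 Wald already gives only 90.5% there.
- That the plain interval wrongly rules out 25% across several outcomes. Only 4/40 changes: at 3/40 both intervals exclude 25%, and at 5/40 both include it.
- That the trial's conclusion is at risk. The 6/40 cut-off is unaffected, and from 7/40 upward the estimates agree within 0.3 points and the limits within 0.1.

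These figures rest on three assumptions: the stopping endpoint is the one estimated, there is no toxicity stop, and enrolment is exactly 27 or 40.

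**What to change.** Replace the estimation sentence in Section XX with text to this effect:

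> For the endpoint that drives the two-stage rule (CR + CRp + PR + marrow clearance of blasts in Cycle 1), the exact two-stage 95% confidence interval (stage-wise ordering, design 2/27, 6/40) and the UMVUE will be reported, with the plain rate x/n alongside. If the trial stops for toxicity at another sample size, the plain rate will be reported with a Clopper-Pearson interval and labelled as unadjusted. The CR + CRp + PR rate may also be reported, with a Clopper-Pearson interval.

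This names the interval type, ties the adjusted result to the endpoint it is valid for, and covers toxicity stops, to which the two-stage formula does not apply.

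The cost is one extra calculation and a higher upper limit at 3 to 6 of 40 (by 4.1 points at 3/40, falling to 0.3 at 6/40). Sample size, stopping boundaries and the decision rule stay as they are.
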